# SCHEMA

**Table 1: Schedule of Events.**

Procedures	Screening	Baseline	6 Weeks**	3 Months**	6 Months**
Informed Consent	X				
Confirm Inclusion/Exclusion	X				
Medical History	X	X	X	X	X
Physical Examination	X	X	X	X	X
Weight	X				
Vital Signs	X				
TSH a	X	X	X	X	X
HbA1c a or Fructosamine	X				
TPO Antibodies a	X				
24 Hour Resting Energy Expenditure (Whole Room Indirect Calorimeter) b		X		X	X
Genomic DNA*		X			
Free T4*		X		X	X
Free T3*		X		X	X
Lipids* a		X		X	X
Serum Storage*		X	X	X	X
Echocardiogram		X		X	X
ThyPro-39 Quality of Life Questionnaire		X		X	X
DXA scan		X			X
Randomization		X			
Study drug dispensation		X	X	X	
Dosing Adjustments			X	X	

- \* Analyses run in the Department of Endocrine Lab
- \*\* +/- 7 days
- a Analyses run in the VCU Health Department of Pathology
- b Visit in Whole Room Indirect Calorimeter may be up to 24 hours

## REVISION HISTORY

Revision history is presented in reverse order so that the information pertaining to the most current version of the protocol is presented first in this section.

Version Number	Date of Issue	Type of Revision	Brief Description of the Revision
Version 1,	01/22/2020	Initial Protocol submission	
Version 2	03/18/2020	Revised version of the initial submission	Added 10.7 added End of Study Directions
Version 3	11/03/2020	Revise version 2.0	
Revise Exclusion criteria 2
 
Current:
 
Graves' disease or thyroid autoimmunity defined by anti-thyroid peroxidase (TPO) antibodies titer > 35 IU/mL
 
Changed to:
 
Graves' disease or thyroid autoimmunity
 
Clarify: TPO antibodies to be analyzed in VCU Pathology Central Lab
 
Current:
 
9.12 ClearSight System
 
This device consists of a small cuff that will be applied over two fingers, and based on the principle of plethysmography records blood pressure, cardiac output, endothelial function and systemic vascular resistance. The measurements will be performed at baseline, 3-months, and 6-months visits.

		
Change to: Deleted Deleted ClearSight procedures for Study visits Baseline, 3 month and 6 month will not be done
 
Current: Study visits Baseline, 3 month and 6 month
 
You will be fitted with five accelerometers (one on each limb plus chest) to record spontaneous movements
 
Changed to : Study visits Baseline, 3 month and 6 month
 
You will be fitted with five accelerometers (one on each limb plus chest) to record spontaneous movements (maybe done based upon availability)
 
Study visits Baseline, 3 month and 6 month
 
Accelerometers Fitting - subject will be fitted with five (one on each limb plus chest) to record spontaneous movements.
 
Changed to: Study visits Baseline, 3 month and 6 month
 
Accelerometers Fitting - subject will be fitted with
	
--	--	---	--

		
five (one on each limb plus chest) to record spontaneous movements (maybe done depending upon availability)
 
Current:  Study visits Baseline, 3 month and 6 month
 
Each of the three phenotyping visits will include a 24-hour recording of energy expenditure in the whole room calorimeter.
 
Change to:  Study visits Baseline, 3 month and 6 month
 
Each of the three phenotyping visits will include an up to 24-hour recording of energy expenditure in the whole room calorimeter.
 
Current:  Study visits Baseline, 3 month and 6 month
 
Standardized Meals will be served at 13:00, and at 18:00, each representing 1/3 of the estimated EE with the following macronutrient composition: 50% carbohydrate, 20% protein, 30% fat. Approximate total energy needs for weight maintenance will be

--	--	--

			
calculated using the Mifflin-St. Jeor equation (89). EE recording will be completed at 11:00 of the following day,
 
Changed:
 
Study visits Baseline, 3 month and 6 month
 
Standardized Meals will be served at 13:00 (if already entered in the WRIC), and at 18:00, each representing 1/3 of the estimated EE with the following macronutrient composition: 50% carbohydrate, 20% protein, 30% fat. Approximate total energy needs for weight maintenance will be calculated using the Mifflin-St. Jeor equation (89). EE recording will be completed at approximately 11:00 of the following day,
 
Current:
 
Study visits Baseline, 3 month and 6 month
 
EE recording will be completed at approximately 11:00 of the following day,
 
Change
 
Study visits Baseline, 3 month and 6 month

--	--	--	---

			
EE recording will be completed at 11:00 of the following day,
 
Current:
 
Volunteers will enter the WRIC at 11:00 and will receive standardized meals at 13:00
 
Change:
 
Volunteers will enter the WRIC at the earliest at 11:00 and will receive standardized meals at 13:00 (if already entered in the WRIC),
 
Current: Exclusion Criteria
 
Uncontrolled diabetes (HbA1c > 8% at screening)
 
Change: Exclusion Criteria
 
Uncontrolled diabetes (HbA1c > 8% or fructosamine < 325 mcmol/l in substitution of HbA1c to reflect recent improvement in diabetes control at screening)
 
Current: Exclusion Criteria
 
Weight <50 or >100 Kg;
 
Change: Exclusion Criteria
 
Weight <50 or >150 Kg;

--	--	--	---

Version 4	03/13/2022	
Revision to Version 3 to include provisions to address drug-drug interactions
	
Advice to contact study team in case of new medications, or dose changes in current medications.
 
Reduction to 1.2 mcg/Kg (-25 mcg in case of randomization to the levothyroxine/liothyronine group) of initial study drug dose in patients taking oral semaglutide

Version 5.0	2/2/2023	
Revision to address change in Principle Investigator
 
Changed the name of the Laboratory where samples are separated, aliquot and stored to Department of Endocrine Laboratory
	
Current
 
Principle investigator: [name] MHS
 
Change Deleted [name], MHS. as PI and changed the Principle investigator to [name]
 
Current Serum will be separated by centrifugation, aliquot in 1 mL cryoviales and stored in -80°C freezers In [name] in Sanger Hall changed to
 
Change
 
Serum will be separated by centrifugation, aliquot in 1 mL cryoviales and stored in -80°C freezers In the Department of Endocrine Lab in Sanger Hall

		
Added a Sub investigator
 
Add an unblinded physician
	
Added a Sub investigator [name]
 
Current
 
Dose adjustments will be performed at the 6-week and 3-month follow up visits by an unblinded endocrinologist ([name]) aiming to achieve and maintain a target TSH within the normal range and within <math>\pm 0.5</math> mIU/ml from the baseline (pre-surgery) TSH, according to the scheme in Table 1.
 
Change
 
Dose adjustments will be performed at the 6-week and 3-month follow up visits by an unblinded endocrinologist ([name]) aiming to achieve and maintain a target TSH within the normal range and within <math>\pm 0.5</math> mIU/ml from the baseline (pre-surgery) TSH, according to the scheme in Table 1. Doses will be rounded to the nearest available formulation
 
Current
 
a physician who is board-certified in Endocrinology and Internal Medicine. Additionally, the unblinded physician ([name])
 
Change
 
a physician who is board-certified in Endocrinology and Internal Medicine.

--	--	---	---

		
Analysis of Lipids samples
	
Additionally, the unblinded physician ([name])
 
Current
 
Analyses run in [name]
 
Change
 
Analysis run in VCU Health Department Pathology Laboratory

--	--	-----------------------------------	--

## LIST OF ABBREVIATIONS

Abbreviations	Description of abbreviations
AE	Adverse Event
AM	Morning
BIA	Bio-electrical Impedance Analysis
BMI	Body Mass Index
BMR	Basal Metabolic Rate
°C	Celsius
Cmax	Maximum Plasma Concentration
CRF	Case Report Form
CRSU	Clinical Research Service Unit
CT	Computerized Tomography
DNA	Deoxyribonucleic acid
DSMB	Data and Safety Monitoring Board
DSMP	Data and Safety Monitoring Plan
Echo	Echocardiogram
EE	Energy Expenditure
ENT	Ears, Nose, and Throat
° F	Fahrenheit
FOA	Funding Opportunity Announcement (NIH)
GWAS	Genome-wide association study
HgA1c	Glycated Hemoglobin
IU	International Units
IRB	Institutional Review Board
Kg	Kilogram
kca	kilocalories

LT3	Liothyronine
LT4	Levothyroxine
mcg	micrograms
ml	milliliter
Na-EDTA	Ethylenediamine Tetraacetic Acid
NIH	National Institutes of Health
PET	Positron Emission Tomography
PHI	Protected Health Information
PK	Pharmacokinetics
PM	Night
QOL	Quality of Life
SAE	Serious Adverse Event
Tmax	Time to achieve Cmax
TSH	Thyroid-stimulating hormone
TPO	Thyroid peroxidase
T3	triiodothyronine
Free T4	Thyroxine
UP	Unanticipated Problem
VCU	Virginia Commonwealth University
Wi-Fi	Wireless Networking Technology
WRIC	whole room indirect calorimeter

## 1 BACKGROUND

Hypothyroidism is a common condition, particularly among women (1, 2). Weight gain despite optimal levothyroxine (LT4) replacement therapy is a common and distressful occurrence in hypothyroidism (3), leading to frequent modifications in therapy (4) with negligible improvements and to patients' dissatisfaction. Importantly, weight gain has been consistently recognized as a driver of poor quality of life in hypothyroid patients (3, 5-8). Additionally hypothyroidism is associated with dyslipidemia (9-11) and myocardium dysfunction and increased cardiovascular risk (12-16). There is a need to characterize in detail the changes in energy metabolism in hypothyroidism, and to study the effects of alternative treatment modalities directed to minimize the prevalence and severity of hypothyroid symptoms. Previous studies directed to assess the efficacy of combination liothyronine (LT3)/LT4 therapies aimed to supplement for the loss of endogenous T3 were underpowered, with heterogeneous study populations, and often with inadequate treatment scheme (17-29). Virtually all the professional organizations lament the lack of high quality, definitive data to support or deny the use of combination therapy for the treatment of hypothyroidism (30-32). Post-surgical hypothyroidism represents an ideal model to study the effects of loss of endogenous production of thyroid hormone and of therapeutic modalities because of the absence of confounders due to residual endogenous hormone production and long transition from eu- to hypothyroidism. By combining the study population characteristics with our ability to perform dense phenotyping, and a rigorous study design, we will conduct a proof-of-concept study to characterize the changes in energy metabolism, cardiovascular function, and lipid metabolism before and after thyroidectomy in response to LT4 or LT3/LT4 combination therapy. The results of this study, within the scope of the R21 funding mechanism will define the point estimates of our intervention. This in turn will enable us to: a) define whether a larger study is scientifically warranted, b) provide for the effect size for post-thyroidectomy weight gain to adequately power a large trial which definitely will address the role of combination therapy for the treatment of hypothyroidism, and c) define effect size for secondary and exploratory aims to be applied to a large clinical trial.

Irrespective of the etiology, the treatment of hypothyroidism is based on the replacement of the lack of endogenous production of thyroid hormone. This is commonly accomplished with LT4, which is metabolized by the deiodinase enzymes into T3 that ultimately delivers the hormonal signal to the tissues (30). This strategy is based on the assumption that the action of the deiodinase enzymes is able to deliver adequate T3 to all the tissue targets of thyroid hormone. Experimental and *in vivo* observations have challenged this axiom. The landmark experiments of Morreale d'Escobar in a rodent model of hypothyroidism demonstrated that LT4 alone is not sufficient to restore hypothyroidism in all tissues (33), and only administration of a combination of LT3 and LT4 could provide adequate restoration of T3 (34). On the clinical side, a significant number of patients, estimated in up to 40%, complain of residual symptoms attributed to hypothyroidism despite achieving the therapeutic goal of normalization of the Thyroid Stimulating Hormone (TSH) (3). Common symptoms include weight gain, cold intolerance, sluggishness, and "mental fog" (35). The persistence of hypothyroid symptoms has been attributed to an insufficient delivery of T3 to the target tissues because of the loss of

the T3 produced by the thyroid (estimated to be 20-30 mcg/day) (36) or to a deficit in peripheral conversion of T4 into T3, possibly due to a common polymorphism of the type 2 deiodinase gene (37). Importantly, weight gain is considered the major driver of patients' dissatisfaction (3, 5-8). The use of LT3/LT4 combination therapy was proposed to provide a more "physiologic" replacement and several clinical trials have been conducted (17-29); however, the results are inconsistent and no clear evidence has emerged. This is likely due to low power, different therapeutic regimens, and to the heterogeneity of the study populations, which were mostly composed of individuals with hypothyroidism secondary to autoimmune thyroid disease, which often have residual endogenous thyroid hormone production. In a crossover study, the substitution of desiccated thyroid extracts (DTE) for LT4 resulted in 1.27 Kg weight loss (38). Importantly, patients who lost weight on DTE therapy had a significant improvement in symptoms. Moreover, a secondary analysis of the largest LT3/LT4 trial indicated that carriers of the Thr92Ala D2 were more likely to have worse quality of life at baseline, and more robust response to LT3/LT4 combination therapy (39). In a crossover intervention, we observed that the substitution of LT3 alone for LT4 resulted in significant weight loss and lowering of cholesterol (40). Collectively, these data support the hypothesis that increased serum T3 levels as result of T3-containing therapeutic regimens enables weight loss, reduction in cholesterol, and possibly improvement in quality of life in hypothyroid patients.

Post-surgical hypothyroidism is unique because patients become acutely devoid of endogenous thyroid hormone production, transitioning from a state of euthyroidism to hypothyroidism entirely dependent on exogenous thyroid hormone replacement. To this end, this form of hypothyroidism represents an ideal experimental platform to study the effects of loss of endogenous thyroid hormone production and of the response to therapy. Importantly, recent guidelines for the treatment of thyroid cancer have significantly reduced the need for thyroid hormone suppressive therapy, and the majority of patients undergoing total thyroidectomy for differentiated thyroid cancer are treated with replacement therapy aimed to normalization rather than suppression of the Thyroid Stimulating Hormone (TSH) (41). Surprisingly, little information is available on the changes in body weight and composition following thyroidectomy, and no thyroid hormone replacement therapy study has selectively recruited patients post-thyroidectomy. The reported weight gain within a year of thyroidectomy ranges from none to almost 3 Kg (42-47). These differences are likely due to retrospective nature of the analyses, methodological shortcomings, and inclusion of patients with pre-existing thyroid dysfunction.

## 2 RATIONALE

### 2.1 Levothyroxine/Liothyronine (LT4/LT3) combination therapy

Contrary to a smaller longitudinal study (48), Gullo and co-workers have demonstrated that patients on LT4 therapy have lower T3 levels than controls (49). We have shown that pharmacoequivalent doses of LT3, able to achieve the same TSH as LT4 (50), result in high-normal serum T3 levels and that LT4 alone results in serum T3 levels at the low end of the normal range (40). The increase in serum T3 levels (and as a consequence, its increase at the target tissue level) is a likely explanation for the beneficial metabolic effects of LT3 monotherapy. To this end, the addition of LT3 to the LT4 therapy regimen has been proposed as a means to overcome the lack of endogenous thyroid hormone production of T3. The definition of LT3 pharmacokinetics PK) is thus a necessary preliminary step to design a therapy which can provide adequate amount of exogenous T3 to maintain the serum levels within the normal range and to minimize T3 serum level fluctuations above and below the target range. The current data on the LT3 PK are not clear, with an estimated half-life ranging from 6 to 22 hours (51-53). The wide range is in part explained by different experimental protocols and dated hormonal assays. We revisited this question by assessing LT3 kinetic and terminal elimination in a group of patients treated with LT3 alone in preparation for nuclear medicine procedures for thyroid cancer (NCT01441154, PI [name]). Study patients were treated with LT3 0.6 mcg/Kg/day in three daily doses (average dose  $18.8 \pm 4.5$  mcg) (50) for four weeks before undergoing last dose PK analysis and terminal elimination. In this population, the kinetics of LT3 can be described by a two-component (fast distribution and slow elimination) model with a distribution half-life of 1.1 hour and an elimination half-life of 28.4 hour. The Tmax was reached at  $1.8 \pm 0.5$  hour from the LT3 administration, with a Cmax of  $324.0 \pm 63.3$  ng/dl. Based on these observations, we have developed a model to assess the effects of 10 mcg LT3 substitution for 25 mcg of levothyroxine on serum T3 levels, sufficient to increase the serum T3 levels. While a single administration would result in significant fluctuations of T3 levels, a twice daily administration regimen will provide more stable T3 serum levels, well within the normal range throughout the day. The therapeutic scheme adopted in this proposal is thus based on these preliminary data.

### 2.2 Experimental approach

This proposal is based on the premise that thyroidectomized patients on levothyroxine replacement therapy represent an ideal experimental model to study the pathophysiology of hypothyroidism due to the lack of endogenous thyroid hormone production. To this end, we intend to perform dense phenotyping in thirty patients with clinical indications for total thyroidectomy at baseline (pre- surgery), and while on LT4 or LT4/LT3 combination therapy for a 6-month period aimed to restore the individuals' TSH level prior to the surgery. The recruitment will be primarily performed from patients undergoing evaluation in the multidisciplinary thyroid neoplasia clinic and through ENT at Virginia Commonwealth University, but the study information will be disseminated among local endocrinologists, and self-referral will be allowed.

## 2.3 Whole-room indirect calorimeters

The indirect calorimeter instruments and techniques allow for non-invasive real-time recording of energy expenditure and respiratory quotient by measuring oxygen consumption and carbon dioxide production. In comparison with alternate forms of measuring energy expenditure (the historically-used metabolic carts and portable calorimeters), the whole room calorimeters overcome the issues of: 1) Low accuracy due to environmental interference (relative humidity, oxygen and carbon dioxide concentration in the testing room, presence of study personnel); 2) Inconvenience of using a face mask or a canopy hood which limit the duration of the observations and the flexibility of conducting tests which require additional sensors or manipulations. Conversely, whole room calorimeters, by allowing free movement of the subject and through controlling and monitoring environmental factors (e.g. temperature, gas concentration in the inflow air), overcome the limitations of the metabolic carts and portable calorimeters. Traditionally, room calorimeters were challenged by the long equilibration period and limited ability of capturing dynamic interventions with time resolution of less than 30 minutes. At VCU, we have recently built and validated a fast-response whole-room calorimeter suite, which allows a fast equilibration period (10 minutes) and recording dynamic changes within 10-15 minutes, favorably comparable to the metabolic cart methods. Additionally, the environmental temperature of our systems can be modulated between 15°C - 30°C (59°F - 86°F) while maintaining an accurate reading. Our room calorimeters are equipped with airtight ports for food administration, Television set, a toilet, and Wi-Fi connectivity, which enable more comfortable and longer studies, as well as direct observation of acute (minutes to hours) effects of pharmacologic interventions on energy expenditure and substrate utilization. The flexibility of the VCU whole-room indirect calorimeter system allows for continuous and noninvasive monitoring of energy expenditure, and other parameters such as heart rate and skin temperature, while the volunteer is in a comfortable environment.

## 3 TRIAL OBJECTIVES

### 3.1 Aim 1: To characterize changes in energy metabolism following thyroidectomy in response to LT3/LT4 vs. LT4 therapy.

Historically, the measurement of energy expenditure (EE) by indirect calorimetry has been used as an index of thyroid function (57). While overt thyrotoxicosis and hypothyroidism are associated with dramatic extremes in EE, small differences sufficient to generate significant weight changes (40) or small variations in LT4 dose fall below the detection of the ventilated hood (“metabolic cart”) technique (58). Additionally, the ventilated hood method does not allow for prolonged recordings, negating the opportunity to reliably measure the entire spectrum of the EE. Interestingly, a recent report indicated that the metabolic signature of chronic calorie restriction is low T3 and decreased sleeping EE (59). The whole room indirect calorimeter (WRIC) technique enables recordings of the entire spectrum of EE components, including resting and sleeping EE, spontaneous movements, and thermic effect of food in a near free-living environment (60). For our WRIC system, we have recently devised and validated a data

analysis algorithm to overcome the suboptimal temporal resolution issue associated with traditional WRICs. This method minimizes the latency between events and response in EE recordings and enable truly minute-by-minute real-time monitoring capability of WRIC (61). Additionally, the continuous recording of the respiratory quotient (RQ) during controlled fasting enables us to assess substrate utilization and metabolic flexibility, which correlates well with the risk of developing metabolic complications from obesity (62). The real-time monitoring capability of WRIC, coupled with precise event annotation and timestamping as well as the wearable sensors that collect other physiological data simultaneously, allows for analysis of each component of EE. For example, the thermic effect of food can be found by aggregating the post-prandial EE 4-hours after the meal time. Sleeping/wake onset times can be detected using wearable activity sensors (63) and sleeping EE can be found by aggregating EE between sleep time and wake onset time. While no exercise will be conducted in our study, we also plan to monitor minute-by-minute activity counts and assess the impact of spontaneous activities on EE in our analysis. The optimized temporal response of our WRIC system, and expertise in wearable data collection and analysis, will in turn make the VCU whole room indirect calorimeter system uniquely poised to record small differences in the EE and its components. For the purpose of this study, we will perform 24-hour recordings of EE in the VCU WRIC which has a precision of 0.05 Kcal/min. In preliminary experiments performed in a group of liver transplant patients with or without non-alcoholic fatty liver disease (NAFLD), we were able to detect a significant difference in RQ during controlled fast (Figure 4) indicating that NAFLD adversely affects metabolic flexibility in this population. These data show that the VCU WRIC system is uniquely positioned to detect small differences in EE components which over time can result in significant weight changes. In our study design, study participants will undergo a total of three 24-hour EE recordings before, three, and six months after total thyroidectomy while on LT4 alone or LT3/LT4 therapy. Weight will be measured by a stadiometer at the end of each EE recording, following 15-hour fasting, after voiding. Body composition will be measured by DXA scan at baseline and at the completion of the study.

**Expected results.** We predict that patients undergoing total thyroidectomy treated with LT4 alone will experience a significant weight gain over a six-month period following the procedure despite adequate replacement therapy. Treatment with LT3/LT4 combination therapy will prevent weight gain while achieving TSH levels similar to the LT4-only group. Moreover, the longitudinal assessment of EE will provide novel and clinically relevant information on the effects of surgical hypothyroidism and its treatment on EE and its components. Collectively, the data will enable us to define in detail the changes in weight and energy balance in its components, and body composition due to the lack of endogenous thyroid hormone production, and the response to therapies.

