Given the sample size of 15, we further estimate the statistical power of detecting differences in energy expenditure. Based on our recent pilot study on assessing resting metabolic rate (RMR) across 12 healthy, normal weight subjects (including both sexes, BMI:  $24.1 \pm 2.9$ , age: 25~71), we estimated that the within-subject variation in RMR is less than 0.15 kcal/min, whereas our instrument variation is less than 0.05 kcal/min within a day. Therefore, using the same cross-sectional design of 15 patients per arm, assuming we can detect a difference in RMR of 0.14 kcal/min (which is more than two times of the instrument precision), we can achieve a sufficient power of 80% with a significance level of 0.05 using a one-sided two-sample t-test.

For the exploratory aims, we plan to assess if the response to ThyPRO-39, a QoL questionnaire/instrument would yield significant difference between subjects on LT4/LT3 vs LT4 alone. We are also interested in

assessing potential genetic heterogeneity underlying the treatment group effect. More specifically, we would model the QoL endpoints using the ANOVA models incorporating treatment effect (LT4/LT3 vs LT4 alone), Thr92Ala D2 polymorphism (Thr/Thr, Thr/Ala, vs Ala/Ala), and their interaction effects. This would depict a better picture of which genetic group might benefit the most from LT4/LT3 combo therapy. This ANOVA modeling strategy can be extended in a straightforward manner to ANCOVA to assessing changes in other outcomes of interest, adjusting for potential genetic heterogeneity, as well as serum T3 level, and other important covariates.

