## **9.4 Energy Expenditure Recordings**

Each of the three phenotyping visits will include an up to 24-hour recording of energy expenditure in the whole room calorimeter. The room calorimeter is a 10' x 10' x7'6" room with a window and transparent plexiglass wall. The room is fitted with TV, phone, hospital bed, small desk, a toilet behind a privacy screen and a vanity. Meals are passed through an air lock port. The room is fitted with Wi-Fi and the door has no lock. The enclosed space may cause some minimal discomfort and the ventilation can be noisy, non-dissimilar to a commercial airplane. Study volunteers will be instructed they can step out the room and withdraw from the study at any time, and there is no lock in the calorimeter's door. Volunteers will enter the WRIC at the earliest at11:00 and will receive standardized meals at 13:00 (if already entered in the WRIC), and at 18:00, each representing 1/3 of the estimated EE with the following macronutrient composition: 50% carbohydrate, 20% protein, 30% fat.

Approximate total energy needs for weight maintenance will be calculated using the Mifflin-St. Jeor equation (89). EE recording will be completed at approximately 11:00 of the following day.

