## **9.7 Accelerometers**

The accelerometers are sensing devices that measure a moving object's acceleration and can detect frequency and intensity of human movement. They are very similar to "Fitbit" or other exercise recording devices. Maybe done depending upon availability

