## Appendix A

**BMR formula** is as follows:

BMR (kcal / day) = 10 \* weight (kg) + 6.25 \* height (cm) – 5 \* age (y) + s (kcal / day) , where s is +5 for males and -161 for females.

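### The only derivation given for thermic effect of food is a 4-hour sum of post-meal energy expenditure with nothing subtracted, so it is mostly resting expenditure and carries over any resting-rate difference between arms

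*Combined protocol and SAP*

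**What the plan says.** Section 3.1 justifies the whole-room calorimeter by its ability to record all components of energy expenditure (EE), "including resting and sleeping EE, spontaneous movements, and thermic effect of food in a near free-living environment". For thermic effect of food it offers one derivation, introduced as an example: "the thermic effect of food can be found by aggregating the post-prandial EE 4-hours after the meal time". Neither 3.1, 9.4, the visit descriptions in 10.3 to 10.6 nor the Statistical Methodology text of the Protocol Summary subtracts resting, fasting or pre-meal expenditure.

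Under 9.4 the evening meal is at 18:00. The 13:00 meal is given only if the participant is already in the room. Meals are sized from a predictive equation (formula in Appendix A), "each representing 1/3 of the estimated EE with the following macronutrient composition".

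For sleeping expenditure, 3.1 states: "Sleeping/wake onset times can be detected using wearable activity sensors". Expenditure is then summed between the two times. The only activity sensors in the procedures are the accelerometers, of which 9.7 says "Maybe done depending upon availability"; 10.3, 10.5 and 10.6 repeat this for all three phenotyping visits. No fallback sleep window is given.

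**The concern.** Thermic effect of food is the increment in expenditure caused by a meal. A plain sum over the four hours after eating also contains the resting expenditure and movement that would have occurred without it. A treatment effect on resting rate would then be counted twice: once as resting expenditure and again as an apparent effect on diet-induced thermogenesis. Analysing change from baseline does not help, because a treatment effect on resting rate is itself a change from baseline.

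The Expected results under Aim 1 promise findings on EE and its components, and section 4 says the point estimates will be used to choose outcomes for, and to size, a larger trial. A thermic-effect estimate that mainly restates resting rate would mislead that step.

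**Working it through.** **Inputs from the documents.** Four-hour window (3.1). Meal equal to one third of estimated EE (9.4). Appendix A: 10 × weight + 6.25 × height − 5 × age + s, with s = −161 for women. Mean weight 69.7 kg and age 49.3 y in the prior crossover study, and a resting metabolic rate (RMR) difference of 0.14 kcal/min, variation 0.15 kcal/min, 15 per arm, one-sided 0.05 (all Statistical Methodology).

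**Assumptions.** Height 165 cm. Thermic effect t = 5-15% of meal energy. Activity multiplier f = 1.0-1.5 on the Appendix A value, because 9.4 states none. Movement is ignored.

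**1. The plan's own figure.** A two-sample t-test with difference 0.14, SD 0.15, 15 per arm and one-sided 0.05 has power 80.2%, which reproduces the stated 80%. The documents give no figure for thermic effect.

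**2. Resting share of the sum.** With B the daily resting expenditure, four hours of rest is B/6 and the thermic effect is t × f × B/3. The share is (B/6) / (B/6 + t f B/3) = 1 / (1 + 2 f t), whatever the body size.
- f = 1.0, t = 0.10: 1/1.20 = 83%
- f = 1.0, t = 0.05: 1/1.10 = 91%
- f = 1.5, t = 0.15: 1/1.45 = 69%

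**3. Example in kcal.** B = 10 × 69.7 + 6.25 × 165 − 5 × 49.3 − 161 = 1,320.75 kcal/day, or 0.917 kcal/min. Rest over 240 min is 220 kcal. With f = 1.0 the meal is 440 kcal and the thermic effect at 10% is 44 kcal.

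**4. Carry-over.** 240 × 0.14 = 33.6 kcal added to the sum with no change in thermic effect.
- f = 1.0, t = 0.10: 33.6/44.0 = 76%
- f = 1.0, t = 0.05: 33.6/22.0 = 153%
- f = 1.5, t = 0.15: 33.6/99.1 = 34%

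The carry-over is proportional to the resting difference: at 0.07 kcal/min it is 16.8 kcal, or 38% of 44. The percentages also depend on body size, since 33.6 kcal is fixed while the meal is not.

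**5. Consequence for a test.** Suppose true thermic effect is equal in both arms, the resting difference is 0.14 kcal/min with SD 0.15, and thermic effect has an assumed SD of 10-20 kcal. The SD of the sum is √(36² + 10²) = 37.4 to √(36² + 20²) = 41.2 kcal, where 36 = 240 × 0.15. In simulation, a one-sided 5% test on the sum was significant in 70-77% of trials. After subtracting 240 × each participant's resting rate, measured with error 0.05 kcal/min, it was significant in about 5%.

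**The case against.** **Status of the sentence.** It is an illustration in a paragraph about what the calorimeter can do, not an endpoint definition, and silence about a baseline does not mean none will be used. This stands: a reader might infer that the plan prespecifies an erroneous endpoint, and it does not. But no other derivation is given, so an analyst must follow this wording or choose a method later.

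**Reach.** A reader might infer that the primary comparison or its power is compromised. The Endpoints list names weight and energy expenditure as primary and does not name thermic or sleeping expenditure. EE power is given for RMR only.

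**Size.** The plan's words are "assuming we can detect a difference in RMR of 0.14 kcal/min", a choice tied to instrument precision. It equals 0.14 × 1,440 = 202 kcal/day, about 15% of resting expenditure in the example. The prior crossover found no significant resting difference even with full LT3 substitution, and the plan does not expect the combination to exceed pure LT3. So the documents do not support saying that the trial will show a false difference. The 0.15 in step 5 is also described as within-subject; a larger between-subject SD would lower the 70-77%.

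**Remedy.** Subtracting rest leaves movement in, and no awake resting period is scheduled. The first is true and should be stated. On the second, the planned RMR comparison already needs a resting rate from these recordings, and Table 5 has participants fasting from 18:00 until about 11:00.

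**Sensors.** Section 3.1 says sleep times can be found this way, not that they must be. No link between sensor availability and arm is shown, so arm bias does not follow; the gap is an unspecified fallback.

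**Conclusion.** The concern holds for a component measure. Followed as written, the 3.1 derivation gives a quantity that is 69-91% resting expenditure over the assumed ranges, and it moves by 240 min × any resting-rate difference between arms. The expected carry-over follows from the definition of the sum; a true thermic-effect difference could offset or add to it. Its size depends on a resting difference that the plan does not predict. The 33.6 kcal, or 34-153% of the assumed thermic effect, is an illustration at the detectability threshold for one example body size. Height, thermic-effect percentage and activity multiplier are assumptions, but resting expenditure is the majority throughout. The sleep-sensor matter is secondary: sleeping expenditure could be missing or method-dependent for some patients or visits.

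**What to change.** In 3.1, define thermic effect of food as EE over the 4 hours after the 18:00 meal, which is served at every phenotyping visit, minus 240 min × the fasting resting rate from the same recording. Use the same resting rate as in the RMR comparison. Report it also as a percentage of meal energy. State that movement in the window remains in the estimate unless activity data are available to adjust for it.

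For sleeping expenditure, name one rule that needs no sensor and apply it to all patients and visits. A fixed clock window is one example; the choice is the sponsor's. Use the accelerometers as a supplementary check.

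The cost is a few sentences and no new procedure, provided the resting rate for the RMR comparison is itself defined. The downside is some added measurement noise: at an instrument variation of 0.05 kcal/min, the subtracted term contributes 240 × 0.05 = 12 kcal of error that the raw sum does not have.
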